10.2 Sample size

The ICE model was anticipated to reduce total cost of care by 25% compared to usual care (52–54). Because of the lack of peer-reviewed literature evaluating the economic impact of IPT, an effect similar to ICE was assumed for the purpose of performing power calculations. We will need to enroll a total of 3,096 patients (1,032 per arm) to conservatively detect a change in spending of 20% between either treatment arm and usual care with 80% power and an alpha of 0.05, with 33 clusters, and 10% loss to follow-up over the 12-month study period. Our results are robust to a standard deviation of 1.25 times the mean and an ICC value of 0.01. Given the substantially larger sample size required for our economic analyses, we powered our trial on the basis of this outcome, which would also give us more than 98% power to detect a 6-point change in ODI between each intervention arm and the usual care arm.

11. Risk Protection

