10.1 Analysis plan

All analyses will be performed using intention to treat principles based on study arm with which a subject is assigned at study enrollment and regardless of whether or not all protocol steps have been completed. We will report means and frequencies of pre-randomization variables separately by study arm. Comparison of these values will be made with generalized estimating equations to adjust for the block and cluster randomized design.

Because cost data in healthcare is not normally distributed (32) due to significant zero data representing subjects for whom there is little to no cost, we will have to model the data accordingly. We will evaluate the two primary outcomes, total cost of care, using generalized estimating equations with gamma distributed errors and an identity link function which can account for a positively skewed distribution. Changes in ODI from baseline to three months will be compared for the treatment arms using generalized estimating with normally distributed errors and an identity link function. All models will adjust for age and sex, account for the cluster and block randomized study design and include fixed effects for the 3 different delivery networks that were used for recruitment. In secondary analyses, we will repeat our models adjusting for unmatched confounders that remained despite randomization. Our primary analyses will compare each of the two treatment arms separately with usual care (i.e., ICE compared with usual care and IPT with usual care). Because we are evaluating two primary

outcomes, we will use a Bonferroni-corrected two-tailed type 1 error of 0.025. Analysis of secondary outcomes will also be performed using generalized estimating equations with error distributions and link functions appropriate to the outcomes being evaluated.

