As resource utilization and ODI were collected at multiple time points, we will also evaluate non-missing cost and ODI data from each time point using a repeated measures design. In specific, we will use generalized estimating equations, with link functions and error distributions appropriate to the study outcomes, to assess changes in outcomes over the 12 months of follow-up, while accounting for correlations in the repeated measurements. For spine-related health spending, these analyses will be conducted using the time intervals at which raw data were collected as well as after converting estimates to evenly-spaced months. Because cost data in healthcare is not normally distributed with zero values for participants with no resource utilization during follow-up, we will winsorize estimated costs at the 95th percentile in secondary analyses. We will report relative spending differences with confidence intervals and a two-tailed p value. As a sensitivity analysis, we will conduct a complete-case analysis on all non-missing values.

Exploratory analyses will be performed evaluating the effect of the interventions on cost in various strata of clinical interest, including age, sex, STarT Back risk group, location of pain, and whether or not this was the subject's first pain episode. We will also evaluate the percentage of subjects in each arm with a decrease in ODI of six points at three, six, and twelve months of follow-up.

2 Sample size

The ICE model was anticipated to reduce total cost of care by 25% compared to usual care (52–54). Because of the lack of peer-reviewed literature evaluating the economic impact of IPT, an effect similar to ICE was assumed for the purpose of performing power calculations. We will need to enroll a total of 3,096 patients (1,032 per arm) to conservatively detect a change in spending of 20% between either treatment arm and usual care with 80% power and an alpha of 0.05, with 33 clusters, and 10% loss to follow-up over the 12-month study period. Our results are robust to a standard deviation of 1.25 times the mean and an ICC value of 0.01. Given the substantially larger sample size required for our economic analyses, we powered our trial on the basis of this outcome, which would also give us more than 98% power to detect a 6-point change in ODI between each intervention arm and the usual care arm.

References

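### The cost outcome is powered at alpha 0.05 but tested at two-tailed 0.025, where power for a 20% reduction is about 72%, not the stated 80%

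*Combined protocol and SAP*

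**What the plan says.** Protocol section 10.2 and SAP section 2 (Sample size) carry the same calculation. It expects an effect of 25% ("The ICE model was anticipated to reduce total cost of care by 25% compared to usual care") and assumes a similar effect for IPT. The trial is then sized for a smaller one, with 3,096 patients, 1,032 in each arm, so that it can "conservatively detect a change in spending of 20% between either treatment arm and usual care with 80% power and an alpha of 0.05". The SAP gives the remaining terms as "with 80% power and an alpha of 0.05, with 33 clusters, and 10% loss to follow-up". On variability, both sections say: "Our results are robust to a standard deviation of 1.25 times the mean and an ICC value of 0.01". Both also say that cost determined the trial's size, because the ODI outcome needed far fewer patients.

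The significance level for the analysis is set elsewhere. Protocol section 10.1 and SAP section 1 (Analysis plan) compare each intervention arm separately with usual care and, because there are two primary outcomes, state that "we will use a Bonferroni-corrected two-tailed type 1 error of 0.025".

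**The concern.** The calculation that fixed enrolment uses one significance level and the planned test uses a stricter one. Neither document acknowledges the difference or gives power at 0.025, whether for the 20% used for sizing or the 25% anticipated. The formula, the sidedness of the 0.05, and whether the SD scales with each arm's mean are also unstated, so a reader cannot convert the figure with certainty.

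Cost is the outcome the trial was sized for. Anyone interpreting a null cost result will look to the stated 80%, which overstates the chance of detecting a 20% reduction at the threshold actually applied.

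**Working it through.** **Inputs from the documents.** 1,032 enrolled per arm; 10% loss; 33 clusters randomised 1:1:1 (protocol section 7.1), so 11 clinics per arm; SD 1.25 times the mean; ICC 0.01; change of 20%; alpha 0.05 for sizing and two-tailed 0.025 for testing.

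**Assumptions of mine.** Normal approximation, two-sided test, equal clinic sizes, SD 1.25 times each arm's own mean. With the usual-care mean set to 1, the SDs are 1.25 and 1.25 × 0.80 = 1.00.

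**Effective sample size per arm**

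- Analysed: 1,032 × 0.9 = 928.8; per clinic 928.8/11 = 84.4
- Design effect: 1 + (84.4 − 1) × 0.01 = 1.834
- Effective n: 928.8/1.834 = 506.3

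**Reproducing the plan at two-sided 0.05**

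- Standardised effect: 0.20/√[(1.25² + 1.00²)/506.3] = 2.811
- Power: Φ(2.811 − 1.960) = 80.3%, against the stated 80%
- Size: n₀ = (1.960 + 0.842)² × (1.25² + 1.00²)/0.20² = 503. Solving n = n₀ × [1 + (n/11 − 1) × 0.01] gives 917 analysed, and 917/0.9 = 1,019 enrolled per arm. The stated 1,032 is within 1.3%.

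**Same inputs at two-sided 0.025 (critical value 2.241)**

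- 20% reduction: Φ(2.811 − 2.241) = 71.6%
- 25% reduction: intervention SD 1.25 × 0.75 = 0.9375; 0.25/√[(1.25² + 0.9375²)/506.3] = 3.600; Φ(3.600 − 2.241) = 91.3%
- Reduction detectable with 80% power: 21.7%

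**A check that does not need the SD or ICC.** Any normal-theory design with exactly 80% power at two-sided 0.05 has Φ(1.960 + 0.842 − 2.241) = 71.2% at two-sided 0.025.

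**Sensitivity for the 20% reduction**

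| Version | Two-sided 0.05 | Two-sided 0.025 |
|---|---|---|
| SD 1.25 × each arm's mean | 80.3% | 71.6% |
| Log scale: ln(1/0.8)/√(2 × 1.25²/506.3) = 2.840 | 81.1% | 72.5% |
| SD 1.25 × usual-care mean in both arms: 0.20/√(2 × 1.25²/506.3) = 2.546 | 72.1% | 62.0% |
| First row, t reference with 20 df (22 clinics) | 76.2% | 65.2% |
| First row, ICC 0.005 (assumed) | 89.2% | 83.1% |
| First row, SD 1.1 × mean (assumed) | 89.2% | 83.0% |

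The common-SD version reaches about 80% only with a one-sided 0.05 (81.6%). At 0.025 it gives 82.7% for a 25% reduction; the log-scale version gives 92.2% for 25% and 80% power at a 21.5% reduction.

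**The case against.** The strongest reply is that 72% rests on an inferred formula. The sample size section gives no formula or sidedness, and its wording about robustness may mean that 1.25 and 0.01 are limiting values. If so, 72% is a worst case. Under the same formula, 80% power at 0.025 is recovered once the ICC is about 0.0063 or lower, or the SD about 1.14 times the mean or lower (values solved for, not in the documents). This caveat stands and must accompany the figure. Two things limit it. Using 1.25 and 0.01 as inputs nearly reproduces the stated size, and the smaller assumed values in the table would give about 89% at 0.05, not the 80% claimed. Reading 0.05 as one-sided does not help either: the version that then fits gives 62.0% at the actual test level.

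The plan also speaks of a change, not a reduction. With arm-specific SDs a 20% increase has only about 63% power at two-sided 0.05, so the inferred formula supports 80% in one direction only. The plan's hypothesis is a decrease, so the mismatch is unaffected.

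It can also be said that the arithmetic is sound at the alpha it names, that power is high for the anticipated effect, and that the document is final and can no longer alter enrolment. All three are fair. They limit the consequence, but the stated power still belongs to a test that the plan does not perform.

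**Conclusion.** The concern holds. Sizing at 0.05 and testing at two-tailed 0.025 are in plain conflict in both the protocol and the SAP. On the reading that best reproduces the sponsor's own sample size, power for a 20% cost reduction is about 72%, so a true effect of that size would be missed about 28% of the time rather than 20%. The drop to about 71–72% follows for any normal-theory design with 80% power at two-sided 0.05. The absolute level depends on unstated assumptions: 62% with a common SD, 65% with a t reference, and about 83% if the ICC or SD is lower than stated.

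The effect on the trial is moderate, since power exceeds 90% for the anticipated 25% reduction under the inferred formula. This should be fixed, but it does not threaten the design.

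**What to change.** In protocol section 10.2 and SAP section 2, keep the existing calculation, name its formula, sidedness and SD assumption, and say whether 1.25 and 0.01 are inputs or upper limits. Then add a sentence such as:

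> At the two-sided 0.025 level used for each primary outcome, the same sample size gives about 72% power for a 20% reduction, about 91% for the anticipated 25% reduction, and 80% for a reduction of about 22%.

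The sponsor should confirm or replace these figures using its own formula. The word *conservatively* can stay if it is tied to its apparent meaning, namely 20% rather than the anticipated 25%.

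The cost is one sentence and a short clarification in each of two sections, plus one rerun of the power calculation. Enrolment, tests and alpha do not change. The stated power becomes less favourable.

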11.1 Risks Associated with the Inventions Under Investigation

Since the interventions under investigation are accepted forms of treatment for neck and lower back and leg symptoms, it is anticipated that the potential risks to the subjects are the same as for any standard treatment in these areas. If adverse effects occur, we anticipate that appropriate medical care will be provided by the subject's primary care physicians, who will continue to be involved in the care of subjects in all three of the study arms. Systemic red flag symptoms, including leg weakness and urinary incontinence are not expected to occur because enrolled subjects will be screened by their primary care doctors and are required to be low risk at study entrance. However, in the event a red flag symptom occurs, subjects in all 3 arms will be instructed to urgently report this to their primary care physician, who will arrange for triage per standard of care. Adverse events will not be actively solicited but they will be tracked should an event come to the awareness of the investigators.

11.2 Subject Confidentiality

Identifiable research material shall consist of medical records, questionnaires, and data that will be obtained specifically for the study. Identifiable data will be retained and secured in a locked cabinet at each site. In specific, electronic study data will be stored in a 21 CFR part 11 compliant system and all paper documentation with personal health information would be stored in a secured location at each site. Each study site will be individually responsible for complying with all local and state laws, regulations and Human Subjects Committee policies

regarding collection and distribution of subject information. The questionnaire information is not unusually sensitive and will be subject to strict confidentiality safeguards.

Subjects will be informed of the confidentiality of the data and assured that it will be used only in aggregate for statistical purposes, with no identification of individuals. No data beyond what is included in the informed consent will be sought without authorization from hospitals and doctors and without signed medical release from the subjects. All study personnel will be instructed not to discuss any cases with persons other than other study personnel. All hard copies of study records will be kept in locked files to which only study personnel have access.

[figure not shown]
11.3 Reporting requirements

The Site Principal Investigator or Designee will report to the IRB any of the following *adverse events* that occur: 1) during the conduct of the study, 2) after study completion (if study staff become aware), or 3) after participant withdrawal or completion (if study staff become aware).

1. *Unanticipated adverse effects* that are serious and caused by, or associated with, the study treatments (ICE care or IPT care).
2. Breach of confidentiality or violation of HIPAA (e.g., lost or stolen laptop).

Reports will be submitted within 5 working days or 7 calendar days of the date the investigator first becomes aware of the problem. In cases involving serious adverse events, reports will be submitted to IRB within 48 hours of the investigator becoming aware of the event.

12. Study Timeline

STATISTICAL ANALYSIS PLAN

Outcomes

1 Primary Outcomes

The two primary outcomes for the trial will be: (a) spine-related cost of care at one year and (b) change in pain at three months as assessed by the Oswestry Disability Index (ODI, Appendix G). Secondary outcomes will include pain at 12 months, quality of life at 12 months assessed using the EQ-5D, and self-efficacy at 12 months assessed using a scale developed by Lorig et al. (31).

Table 1: Outcomes

Primary	Spine related cost of care at one year Change in pain (measured by ODI) at three months
Secondary	Change in pain (measured by ODI) at one year Quality of life (measured by EQ-5D) at one year Self-efficacy (measured by scale developed by Lorig et. al) at one year

1.1 Spine-Related Cost of Care

Spine-related cost of care will be estimated by applying unit costs incurred by subjects or third-party payers to estimates of resource utilization obtained from subject-reported utilization data (Appendix H). Subject-reported utilization will be collected using monthly checklists for the first three months, then bimonthly for the following nine months, that are based upon the approach recently employed by Fritz et al. (15) and originally developed by Goosens et al. (33). Subjects will be asked about all healthcare services used, including primary care visits, emergency room encounters, hospital admissions, imaging studies (including MR

and CT), prescriptions, and physical therapy services that pertain to spine-related healthcare (14,34).

Data from the utilization checklists will be categorized using Current Procedural Terminology (CPT) and International Classification of Disease (ICD) codes. Medications will be characterized using the Unified Medical Language System® Master Drug Database, Medi-Span®.

Unit cost of these different services will be estimated using publicly available data sources. In specific, for outpatient visits to PCPs, specialists, physical therapists and other providers and for tests and procedures, we will use the Centers for Medicare & Medicaid Services Physician Fee Schedule Look-Up Tool.¹ For hospitalizations, we will use the hospital adjusted expenses per inpatient day value calculated by the Kaiser Family Foundation.² For emergency department visits, we will use estimates from the Medical Expenditure Panel Survey.³ To calculate the average retail price of medications, we will use average retail prices from GoodRx.com.⁴,

1.2 Pain

The ODI is the most commonly used scale for low back pain (35). It is a self-administered questionnaire that has ten topics: intensity of pain, lifting, sexual function, social life, sleep, and ability to walk, sit, stand, care for oneself, and travel. It has been recommended as one of the standardized metrics for research of low back pain based on its ability to quantify functional status in this population (36). The ODI typically takes three to five minutes to complete, and one minute to score (37). Previous studies have evaluated the ODI in pain-free subjects and found that mean score to be 10.19 (35, 38, 39) and those with disability from low back pain is

22.07 (40). Previous studies have indicated that a change in ODI by 6 points is clinically meaningful (41).

2 Other outcomes

2.1 Quality of Life

Quality of life will be assessed by the EQ-5D (Appendix I), which has been shown to be beneficial in describing and valuing health related quality of life (42, 43). It was developed for self-completion, and has been validated against other measures of quality of life, including SF-12 (44). The EQ-5D has been shown to correlate well with low back pain specific measurements, and also be responsive to change (45,46). The instrument consists of a descriptive section and a visual analogue scale. The descriptive section measures 5 dimensions of health (mobility, self-care, usual activities, pain/discomfort, anxiety/depression) with each dimension having 5 levels ranging from “no problem” to “extreme problem”. The visual analogue scale is a self-rated horizontal health scale with end points labelled as “the best health you can imagine” and “the worst health you can imagine”. The raw scores are converted into index scores based on US norms⁵. Previous studies identify a change in EQ-5D index of 0.08 as a minimal important clinical distance (47), and in a study evaluating the sensitivity to change of EQ-5D index with back pain it was seen that after two weeks there was a decrease of 0.21 after treatment; albeit this was in an interventional study that included steroid injections (46). The EQ-5D is also helpful in converting to quality adjusted life years (QALY) to perform a cost utility analysis, and is the most common measure for conversion (37).

2.2 Self-Efficacy

We will evaluate self-efficacy at baseline, six months, and one year. As the focus of this trial is to support those with acute spine pain to prevent the development of chronic pain, measuring self-efficacy both as a predictor and outcome of the treatment arms will be necessary as a metric of self-management for future episodes. We will use Lorig et al.'s self-efficacy scale for individuals with musculoskeletal complaints, which has three subscales that focus on pain, functioning, and other symptoms (31). Because spine-specific pain is already captured with ODI, we will use the "functioning" and "other symptoms" subscales in this trial to measure self-efficacy (Appendix J). The "function" subscale produces an average of 73.27 (s.d. 20.22), and the "other symptoms" subscale produces an average of 55.62 (s.d. 21.64).

2.3 Productivity

We will also evaluate the impact of spine pain on work-related activities by evaluating absenteeism and presenteeism. Absenteeism will be assessed by subject self-report. Time lost from work, or other usual activities, associated with spine pain and all other health problems will be collected and measured. The total number of unplanned work absences will be multiplied by an average employee's daily wage to obtain the cost per participant of work absenteeism. Presenteeism will be assessed using the methods of van den Heuvel, et al (49). Three assertions will be ranked on a scale of 1-5: 1) I achieve all objectives of the job, 2) Job-related tasks come easily to me, and 3) I perform well in my job. The scores will be dichotomized using the median value from all respondents. A study participant will be described as suffering from presenteeism if they are above the median value.

2.4 Other outcomes

We will measure implementation-related outcomes to assess intervention fidelity.

These will include the number of protocol-specified appointments (i.e., Spine Coach, physical therapist, or the Egoscue practitioner) scheduled and attended, the timing of visits and the length of the treatment course, which we originally expected to last 6 to 8 weeks.

Data Collection

Study data will be collected and managed using REDCap electronic data capture tools (50) hosted at Brigham and Women's Hospital. Data will be collected based on the schedule in Table 3. Study subjects will be contacted by email five business days prior to a survey being due for completion to be notified that the survey is available. If the survey is not completed they will be notified again three and five business days after the due date. Should the study subject still not complete the survey, they will have three phone attempts to be reached and guided through completion.

Table 2: Subject Reported Outcome Administration Schedule

Metric	Months After Enrollment												
	0	1	1.5	2	3	4	5	6	7	8	9	10	11
STarT Back Tool	x												
Healthcare Utilization Checklist		x		x	x		x		x		x		x
Oswestry Disability Index	x		x		x			x					x
EQ-5D	x		x					x					x
Self-Efficacy Questionnaire	x							x					x

Statistical considerations

1 Analysis plan

All analyses will be performed using intention to treat principles based on study arm with which a subject is assigned at study enrollment and regardless of whether or not all protocol steps have been completed. We will report means and frequencies of pre-randomization variables separately by study arm. Comparison of these values will be made with generalized estimating equations to adjust for the block and cluster randomized design.

Because cost data in healthcare is not normally distributed (32) due to significant zero data representing subjects for whom there is little to no cost, we will have to model the data accordingly. We will evaluate the two primary outcomes, total cost of care, using generalized estimating equations with Poisson distributed errors and a log link function which can account for a positively skewed distribution. Changes in ODI from baseline to three months will be compared for the treatment arms using generalized estimating with normally distributed errors and an identity link function. All models will adjust for age and sex, account for the cluster and block randomized study design and include fixed effects for the 3 different delivery networks that were used for recruitment. In secondary analyses, we will repeat our models adjusting for unmatched confounders that remained despite randomization. Our primary analyses will compare each of the two treatment arms separately with usual care (i.e., ICE compared with usual care and IPT with usual care). Because we are evaluating two primary outcomes, we will use a Bonferroni-corrected two-tailed type 1 error of 0.025. Analysis of secondary outcomes will also be performed using generalized estimating equations with error distributions and link functions appropriate to the outcomes being evaluated.

Missing data will be accounted for using multiple imputation (51), which has been determined an adequate strategy to minimize both false positive and false negatives in clinical trials. We will perform 20 imputations using Proc MI in SAS with a fully conditional specification. The following variables will be used to perform the imputation: age, study arm, study site, clinic, sex, race/ethnicity, BMI, exercise frequency at baseline, education level, employment status, smoking status, other medical conditions at baseline, number of medications used for spine pain at baseline, length of pain at baseline, number of previous pain episodes, STarT back score, baseline ODI, baseline self-efficacy, baseline EQ-5D, and scores for patient-reported outcomes at every follow-up timepoints (ODI, cost, Lorig self-efficacy scale, and EQ-5D).

As resource utilization and ODI were collected at multiple time points, we will also evaluate non-missing cost and ODI data from each time point using a repeated measures design. In specific, we will use generalized estimating equations, with link functions and error distributions appropriate to the study outcomes, to assess changes in outcomes over the 12 months of follow-up, while accounting for correlations in the repeated measurements. For spine-related health spending, these analyses will be conducted using the time intervals at which raw data were collected as well as after converting estimates to evenly-spaced months. Because cost data in healthcare is not normally distributed with zero values for participants with no resource utilization during follow-up, we will winsorize estimated costs at the 95th percentile in secondary analyses. We will report relative spending differences with confidence intervals and a two-tailed p value. As a sensitivity analysis, we will conduct a complete-case analysis on all non-missing values.

Exploratory analyses will be performed evaluating the effect of the interventions on cost in various strata of clinical interest, including age, sex, STarT Back risk group, location of pain, and whether or not this was the subject's first pain episode. We will also evaluate the percentage of subjects in each arm with a decrease in ODI of six points at three, six, and twelve months of follow-up.

2 Sample size

The ICE model was anticipated to reduce total cost of care by 25% compared to usual care (52–54). Because of the lack of peer-reviewed literature evaluating the economic impact of IPT, an effect similar to ICE was assumed for the purpose of performing power calculations. We will need to enroll a total of 3,096 patients (1,032 per arm) to conservatively detect a change in spending of 20% between either treatment arm and usual care with 80% power and an alpha of 0.05, with 33 clusters, and 10% loss to follow-up over the 12-month study period. Our results are robust to a standard deviation of 1.25 times the mean and an ICC value of 0.01. Given the substantially larger sample size required for our economic analyses, we powered our trial on the basis of this outcome, which would also give us more than 98% power to detect a 6-point change in ODI between each intervention arm and the usual care arm.

References

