7.1 Randomization

Randomization will occur at the clinic level (i.e. subjects will be cluster randomized) in a 1:1:1 ratio to usual care, usual primary care + ICE, and usual primary care + IPT. To ensure adequate balance between the treatment arms with respect to sample size practices will be categorized into blocks of 3 based on the average number of patients with spine pain that they see in a typical week, their location, and/or their provision of other services such as urgent/walk-in care. Because of differences between the delivery networks participating in the trial, the stratification factors may differ by location. Randomization will occur within these blocks.

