9.3 Data Collection

Study data will be collected and managed using REDCap electronic data capture tools (50) hosted at Brigham and Women's Hospital. Data will be collected based on the schedule in Table 3. Study subjects will be contacted by email five business days prior to a survey being due for completion to be notified that the survey is available. If the survey is not completed they will be notified again three and five business days after the due date. Should the study subject still not complete the survey, they will have three phone attempts to be reached and guided through completion.

Table 3: Subject Reported Outcome Administration Schedule

Metric	Months After Enrollment													
	0	1	1.5	2	3	4	5	6	7	8	9	10	11	12
STarT Back Tool	x													
Healthcare Utilization Checklist		x		x	x		x		x		x		x	x
Oswestry Disability Index	x		x		x			x						x

EQ-5D	x		x					x						x
Self-Efficacy Questionnaire	x							x						x

10. Statistical considerations

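### The co-primary three-month ODI model omits baseline ODI as a covariate; adding the subject value with its clinic mean would modestly improve precision and robustness to chance imbalance

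*Combined protocol and SAP*

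**What the plan says.** Protocol 10.1 and the SAP (Statistical considerations, 1 Analysis plan) define the co-primary ODI analysis in the same way: "Changes in ODI from baseline to three months will be compared for the treatment arms using generalized estimating with normally distributed errors". The link is the identity. The covariate rule is also the same in both: "All models will adjust for age and sex, account for the cluster and block randomized study design and include fixed effects" for the three delivery networks. Baseline ODI is not in that list, either as a subject value or as a clinic mean.

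The baseline value will be available. Protocol 9.3 says "Data will be collected based on the schedule in Table 3", and that table schedules ODI at month 0. The SAP also names it among the imputation variables: "STarT back score, baseline ODI, baseline self-efficacy, baseline EQ-5D".

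Two further planned analyses could bring baseline ODI in. In secondary analyses "we will repeat our models adjusting for unmatched confounders that remained despite randomization", with no variables named. In addition, "we will also evaluate non-missing cost and ODI data from each time point using a repeated measures design". Neither is the primary test.

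On design, protocol 7.1 says "Randomization will occur at the clinic level (i.e. subjects will be cluster randomized") in a 1:1:1 ratio, and "practices will be categorized into blocks of 3" using patient volume, location and/or other services. The sample size section gives 33 clusters, hence about 11 clinics per arm.

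**The concern.** Subtracting baseline fixes the slope of follow-up on baseline at 1. When the true slope is lower, the change score carries baseline noise that a covariate would remove, and the estimated arm difference moves with whatever baseline difference chance has produced. Only about 11 clinics are randomized per arm, and blocking does not use ODI, so some baseline difference between arms is to be expected.

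At stake are the width of the interval for one of the two primary outcomes and how far its estimate depends on the realized baseline difference. The secondary adjustment does not settle this in advance, because its covariates depend on the imbalance seen.

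**Working it through.** **The plan's own ODI figure.** The sample size section states more than 98% power for 6 points but gives no ODI SD. With 10% loss, 0.9 × 1,032 = 928.8 subjects per arm, or m = 928.8/11 = 84.4 per clinic. Borrowing the ICC of 0.01, which is stated for spending, the design effect is 1 + 83.4 × 0.01 = 1.834, and the effective n is 928.8/1.834 = 506 per arm. Power then exceeds 98% if the SD of the analysed variable is at most 23.8 (alpha 0.05) or 22.2 (alpha 0.025). The claim is plausible, though it cannot be reproduced exactly.

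**Assumptions not in the documents.** ODI SD s = 15; ODI ICC 0.01-0.05; subject-level correlation r between baseline and follow-up 0.3-0.8; clinic-level correlation rc from r to 1.0.

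**Formulas.** Let b = ICC × s², w = (1 − ICC) × s², Vx = b + w/m and C = rc·b + r·w/m. For each model V is the variance per clinic, and SE = √(2V/11).
- Change score: V = 2(Vx − C). Slope of the contrast on the baseline difference: C/Vx − 1.
- Subject baseline only: β = (rc·b + r·w)/(b + w); V = Vx − 2βC + β²Vx. Remaining slope: C/Vx − β.
- Subject baseline plus clinic mean: V = (Vx − C²/Vx)(1 + 1/(v − 2)). Remaining slope: 0. Here v is the between-clinic residual df: 30 for 33 clinics in one model; 20 for 22 clinics, or for 33 with 11 block effects; 10 for 22 clinics with block effects.

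**One case in full** (ICC 0.01, r = rc = 0.5). b = 2.25; w/m = 222.75/84.4 = 2.64; Vx = 4.89; C = 2.44. Change score: V = 2(4.89 − 2.44) = 4.89 (before rounding), SE = √(2 × 4.89/11) = 0.94. With both covariates: V = (4.89 − 2.44²/4.89)(1 + 1/28) = 3.80, SE = 0.83, which is 12% lower.

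**Results, three arms in one model (v = 30).** Percentages are relative to the change score.

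| ICC | r | rc | Change-score SE | Subject baseline only | Subject + clinic mean |
|---|---|---|---|---|---|
| 0.01 | 0.3 | 0.3 | 1.12 | 19% lower | 18% lower |
| 0.01 | 0.5 | 0.5 | 0.94 | 13% lower | 12% lower |
| 0.01 | 0.8 | 0.8 | 0.60 | 5% lower | 3.5% lower |
| 0.01 | 0.5 | 0.8 | 0.80 | 8% lower | 8% lower |
| 0.01 | 0.5 | 1.0 | 0.69 | 2% lower | 5% lower |
| 0.02 | 0.5 | 1.0 | 0.69 | 8% larger | 3% lower |
| 0.05 | 0.5 | 0.9 | 0.93 | 9% larger | 3% lower |

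Over an even grid of the assumed ranges, subject baseline plus clinic mean runs from about 18% lower to 0.8% larger, with a median of about 5% lower. With v = 20 the worst case is 1.8% larger. With v = 10 the median gain is about 1.4% and the worst case is about 5% larger.

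**Why the clinic mean is needed.** At ICC 0.01, 2.25/4.89 = 46% of the variance of a clinic's mean baseline lies between clinics. If clinic means are more stable over time than individual scores (rc above r), one subject-level slope is too shallow for the arm contrast. At r = 0.5 and rc = 0.8 or 1.0 it leaves a slope of +0.14 or +0.23, so it under-corrects. The clinic mean removes this.

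**Chance imbalance.** With 1,032/11 = 93.8 enrolled per clinic and ICC 0.01, the design effect is 1.93. The 95% range of the baseline difference is ±1.96 × √(2 × 225 × 1.93/1,032) = ±1.8 points (1.4-2.2 for SD 12-18). Multiplied by the change-score slope at r = rc = 0.3, 0.5 and 0.8, the shift is up to 0.7 × 1.8 = 1.3, 0.5 × 1.8 = 0.9 and 0.2 × 1.8 = 0.4 points. At r = 0.5 with rc = 0.8 or 1.0 it is about 0.65 or 0.5.

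**Power for 6 points.** With alpha 0.025, a noncentral t on 20 df and the largest ICC 0.01 SE above (1.12), the change score has 99.7% power. The adjusted model has at least as much.

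**The case against.** The strongest reply is that this is a preference about efficiency. The change score is unbiased over randomization, and power for the plan's target is not in doubt at ICC 0.01. Every size above rests on assumed values, and the larger gains are the favourable cases in which both correlations are low. All of this stands, and it is why the median and the worst case are given with the best case.

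The SAP also says that each intervention is compared separately with usual care, and it does not say how blocks enter. If pairs of arms are fitted separately with block effects, most of the gain goes. This stands too; the gain depends partly on fitting three arms together.

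The secondary adjustment and the repeated-measures analysis lessen the exposure to imbalance. Blocking and network effects, which the ±1.8 points ignores, could reduce it further. But neither analysis is the primary test, and the secondary adjustment does not name baseline ODI.

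A reader might infer that the primary ODI test is biased or underpowered. The documents do not support either. A material loss of power would need an ODI ICC well above 0.01, and the documents give no ODI ICC.

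**Conclusion.** The omission is real and the same in protocol and SAP. Its consequence is a modest loss of precision and some sensitivity to chance imbalance across about 11 clinics per arm; it is not a validity error. Under the assumed SD and ranges, the standard error with both covariates in one three-arm model lies between about 18% lower and 0.8% larger (median about 5% lower). The change-score contrast could move by up to about 0.4-1.3 points with a baseline difference at the edge of its 95% range at ICC 0.01, against a 6-point target.

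Subject baseline alone might look like a sufficient remedy. It is not a sure one, since it can leave a residual slope and can enlarge the standard error. Nor does the point extend to the EQ-5D and self-efficacy models: the plan leaves their details open, so a baseline covariate not named there is not a decision to omit it.

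**What to change.** In protocol 10.1 and the SAP's Analysis plan, pre-specify subject-level baseline ODI and its clinic mean as covariates in the primary three-month and secondary 12-month ODI models, besides age, sex, design and network. Fit the three arms in one model with the two contrasts against usual care, and state how blocks enter. Keep the unadjusted change-score model as a sensitivity analysis.

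Date the change before arms are compared. The document is marked final and refers to ODI collection in the past tense, but does not say whether the comparison has been made. If it has, keep the change score as primary and report the adjusted model as a labelled post hoc sensitivity analysis.

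The cost is wording only; no new data are needed. Estimating the clinic-mean slope raises the standard error by about 2% (√(1 + 1/28), 33 clinics) or 3% (√(1 + 1/18), 22 clinics, or 33 with block effects). The figure is about 6% (√(1 + 1/8)) if pairs of arms are fitted separately with block effects, where the worst case is about 5% larger than the change score. A late change to a primary model also costs credibility.
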